### 10.5.4 Food-Effect assessment

For evaluation of the food-effect, PK data (ln-transformed  $AUC_{0-t}$ ,  $AUC_{0-inf}$ ,  $C_{max}$  and untransformed  $T_{max}$ ) reported under fed conditions (Period 4) and under fasting conditions (for the same dose level) will be compared using ANOVA from SAS®. The ratio (fed/fasting) and 90% geometric confidence interval will also be calculated for  $AUC_{0-t}$ ,  $AUC_{0-inf}$  and  $C_{max}$ .

If 90% CI for  $AUC_{0-t}$ ,  $AUC_{0-inf}$  and  $C_{max}$  are within 80.00% to 125.00% then no food effect will be concluded.

For all analytes, using GLM procedure in SAS, ANOVA will be performed on ln-transformed  $AUC_{0-t}$ ,  $AUC_{0-inf}$  and  $C_{max}$  at the alpha level of 0.05. The model will include Treatment as fixed effect and Subject as a random effect. Inter- and intra-subject coefficient of variation will be estimated. The ratio of geometric means and 90% confidence interval for the ratio of geometric means, based on least-squares means from the ANOVA of the ln-transformed data, will be calculated for  $AUC_{0-t}$ ,  $AUC_{0-inf}$ , and  $C_{max}$ .

```

SAS® codes for ANOVA: fed vs. fasting
PROC GLM data=basepk;
CLASS TREATMENT SUBJECT;
MODEL VAR = TREATMENT SUBJECT;
RANDOM SUBJECT;
LSMEANS TREATMENT / cl pdiff alpha=0.1;
ESTIMATE 'fed - fasting' TRT 1 -1/cl alpha=0.1;

run;
```

---

Additional statistical analysis may be performed.

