### 10.5.2 Assessment of Dose Proportionality

Dose proportionality analysis for  $AUC_{0-t}$ ,  $AUC_{0-\text{inf}}$  and  $C_{\max}$  will be performed (using the power model with mixed procedure from SAS®) considering data under fasting conditions (Periods 1, 2, and 3).

Power model will include the PK parameter as the response variable and dose (mg) as the explanatory variable. For this model, the variable dose will be treated as a continuous variable.

The form of the model is as follows:

PK Parameter =  $a \times \text{Dose}^b \times e^{\epsilon}$ , where  $\text{Dose} \geq 0$ , and  $e^{\epsilon}$  represents the associated error.

Thus, perfect dose proportionality is met when  $b=1$  (ignoring error). This becomes a linear relationship following a natural-log transformation, The mixed effect statistical model will be the following:

$$\ln(P_{ij}) = \ln(a) + b \cdot \ln(\text{Dose}_{ij}) + s_i + \epsilon_{ij},$$

where  $P_{ij}$  is the value in the  $j^{\text{th}}$  period for the  $i^{\text{th}}$  subject for the PK parameter analyzed,  $\text{Dose}_{ij}$  is the dose in the  $j^{\text{th}}$  period for the  $i^{\text{th}}$  subject,  $s_i$  is the random effect associated to the  $i^{\text{th}}$  subject, and  $\epsilon_{ij}$  is the random error in the  $j^{\text{th}}$  period for the  $i^{\text{th}}$  subject. The  $s_i$  and  $\epsilon_{ij}$  values are assumed to be mutually independent and normally distributed.

The estimate of b together with a 90% confidence interval (CI) will be provided (for each PK parameter model), and this will be used to quantify dose proportionality.

---

```

proc mixed data=dataset;
class subject;
model ln_pk_parameter = ln_dose / solution;
random subject;
estimate 'Beta Estimate' ln_dose 1 / cl alpha=0.1;
ods output estimates = estimates;

run;
```

The PK parameter values estimated from the power model will be plotted against dose. This plot will also include individual subject values  $\pm$  SD (separately by dose level).

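### SAP 10.5.4: the food-effect ESTIMATE statement names TRT, an effect not in the model, and the level order that gives its 1 -1 coefficients their sign is not stated

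*SAP*

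**What the plan says.** SAP 10.5.4 sets the target in prose: "The ratio (fed/fasting) and 90% geometric confidence interval will also be calculated" for the two AUCs and Cmax, "based on least-squares means from the ANOVA of the ln-transformed data". No food effect is concluded if the 90% CIs lie within 80.00% to 125.00%.

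The code that follows has these relevant lines:

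- "PROC GLM data=basepk"
- "CLASS TREATMENT SUBJECT"
- "MODEL VAR = TREATMENT SUBJECT"
- "LSMEANS TREATMENT / cl pdiff alpha=0.1"
- "ESTIMATE 'fed - fasting' TRT 1 -1/cl alpha=0.1"

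The block has no ORDER= option. The SAP does not say how TREATMENT is coded in `basepk`, or which treatments that data set holds. SAP 3.3 labels the fasting treatments A, B and C (Periods 1 to 3) and the fed treatment D (Period 4). Protocol 7.4 allows the Period 4 dose to be lower than the Period 3 dose, so the same-dose fasting comparator need not be C.

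**The concern.** There are two faults in one line, plus a related one in its options.

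1. **Effect name.** ESTIMATE refers to TRT, while CLASS, MODEL and LSMEANS use TREATMENT. A contrast cannot be formed on an effect that is absent from the model.
2. **Sign.** Once the name is corrected, `1 -1` means first level minus second level. Which level comes first is not stated. If fasting comes first, the output labelled 'fed - fasting' is fasting minus fed, and nothing in the run signals this.
3. **Interval.** The option on ESTIMATE has the same form as in the PROC MIXED block of SAP 10.5.2, "estimate 'Beta Estimate' ln_dose 1 / cl alpha=0.1", but the food-effect block is PROC GLM. Correcting the name alone should not be relied on to give the 90% CI from ESTIMATE.

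The food effect is one of the two study objectives, and its direction is part of the result. The protocol's own background (4.3.2) reports reduced absorption of resveratrol with a high-fat meal; a reversed ratio would show such a decrease as an increase.

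**Working it through.** The plan states no figure to reproduce here. The check is of the code, followed by an illustration of size.

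**Effect name.** Of CLASS, MODEL, RANDOM, LSMEANS and ESTIMATE, only ESTIMATE contains TRT. TRT is not a leading abbreviation of TREATMENT and is not in the SAP's abbreviation list. Result as written: no contrast from ESTIMATE.

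**Level order.** The codings that the SAP text supplies, in default sorted order:

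| Coding | First level | Second level | `1 -1` gives |
|---|---|---|---|
| Letters, comparator C | C (fasting) | D (fed) | fasting − fed |
| Letters, comparator B | B (fasting) | D (fed) | fasting − fed |
| Letters, comparator A | A (fasting) | D (fed) | fasting − fed |
| Words | fasting | fed | fasting − fed |
| Period number | 3 (fasting) | 4 (fed) | fasting − fed |

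The LSMEANS pairwise difference is also first minus second level, so it has the same direction, though it does not carry the 'fed - fasting' label.

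**Size of a reversal.** On the ln scale, a sign change turns the point ratio R into 1/R and an interval (L, U) into (1/U, 1/L). Thus 0.70 becomes 1/0.70 = 1.43, and 1.50 becomes 1/1.50 = 0.67.

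Inputs for the interval: n = 16 (SAP 3.5), and ratio and intra-subject CV assumed, because the documents give neither for JOTROL. With treatment and subject in the model there are 15 residual degrees of freedom and t(0.95, 15) = 1.753.

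- s_w = √ln(1 + CV²)
- half-width = 1.753 × s_w × √(2/16)

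For CV 30%: s_w = √ln(1.09) = 0.2936, and half-width = 1.753 × 0.2936 × 0.3536 = 0.182. The limits are 0.70 × exp(±0.182) = 0.584 and 0.840. Their reciprocals are 1/0.840 = 1.191 and 1/0.584 = 1.714 (from unrounded values).

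| Assumed CV | fed/fasting (90% CI) | fasting/fed (90% CI) |
|---|---|---|
| 20% | 0.70 (0.62–0.79) | 1.43 (1.26–1.62) |
| 30% | 0.70 (0.58–0.84) | 1.43 (1.19–1.71) |
| 50% | 0.70 (0.52–0.94) | 1.43 (1.07–1.91) |

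A constructed 16-subject paired data set with levels C and D, ratio 0.70 and CV 30%, fitted with treatment and subject, agrees. Coefficients `1 -1` give 1.429 (1.191–1.714). Coefficients `-1 1` give 0.700 (0.584–0.840), which equals the fed/fasting ratio of geometric LS means.

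**Effect on the decision.** 1/0.80 = 1.25, so an interval lies within 0.80 to 1.25 exactly when its reciprocal does. The no-food-effect conclusion cannot change.

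**Data set contents.** If all four treatments were left in `basepk`, the first two levels would be A and B, and `1 -1` would compare 200 mg with 500 mg fasting. That ratio is 200/500 = 0.40 if exposure is dose-proportional. The prose, which asks for the fasting data at the same dose level, already rules this out; the code does not show it.

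**The case against.** The strongest reply is that the planned result does not depend on ESTIMATE. The prose fixes the direction, the model, the 90% level and the source (LS means), and the LSMEANS line names TREATMENT correctly and asks for differences and limits at alpha = 0.1. The block is also a template: `VAR` and `basepk` are stand-ins, so a wrong name will be put right when it is programmed. The reversal needs three things together: a correction of the name only, a coding with fasting first, and no check against the label. The SAP does not tie the letters A to D to data values, and a coding such as 1 = fed, 2 = fasting would make `1 -1` correct.

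Most of this stands, and it limits the consequence. The ratio can still be obtained, and the reversal is conditional. The reversed intervals above belong to the LSMEANS difference, so reporting one as fed/fasting would take a further slip. The analyses are exploratory (Protocol 12.3). The by-treatment summaries (SAP 10.5.1) and the general quality control programme (Protocol 13.3) could reveal a reversal.

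It does not remove the point. The LSMEANS difference follows the same unstated order, so it does not settle the direction. SAP section 1 undertakes to give the analyses in full detail, and also says that changes which leave methods, definitions and rules alone need no SAP revision. The name could therefore be corrected, and the sign settled, without any record.

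**Conclusion.** The concern holds. As written, the only statement labelled as the fed-minus-fasting contrast refers to an effect outside its own model and returns nothing. This rests on the text alone.

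The second part is conditional. If the name alone is corrected and fasting sorts first, the point ratio is reported as its reciprocal, for example 1.43 for 0.70. If fed is ordered first, there is no reversal. The ratios and CVs used to show the size are assumptions.

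Default sorting of class levels, the refusal of an effect missing from MODEL, and the doubt about the interval option on ESTIMATE in PROC GLM are general software behaviour. The code was not run in SAS, so a test run should confirm them.

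Only the reported ratio, its interval and the direction of the food effect are at risk; the 80.00–125.00% conclusion is not. This is a minor correction that should be made.

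**What to change.** In SAP 10.5.4:

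- State the coding and level order of TREATMENT in the analysis data set.
- With order (fasting, fed), write `ESTIMATE 'fed - fasting' TREATMENT -1 1;`.
- Obtain the 90% CI through an option valid in PROC GLM, for example `CLPARM ALPHA=0.1` on MODEL, or from the LSMEANS difference with fasting as the control level and alpha = 0.1.
- State that `basepk` is restricted to Period 4 and the same-dose fasting treatment.
- Add a check that exp(estimate) equals the fed/fasting ratio of geometric LS means.

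The cost is a few lines of code and one test run to confirm that the contrast and its 90% CI are produced. It needs no new data and does not change the estimand.

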### **10.5.5 Urine PK analysis**

Summary statistics will be used to describe urinary excretion of resveratrol, resveratrol-3-glucuronide, resveratrol-4'-glucuronide, and resveratrol-3-sulfate.

Additional statistical analysis may be performed.

---

**11. Percentages and Decimal Places**

If not otherwise specified, the following rules will be applied, with the exception of PK tables and listings described below:

Percentages will be presented to one decimal point.

Percentages equal to 0 or 100 will be presented as such without a decimal point.

Minimum and maximum will be presented with the same precision as the original values and, mean, standard deviation, and median will be presented with one more decimal place than the original values.

All digits will be used for pharmacokinetic and statistical PK calculations. For PK tables and listings, the final reportable results or data will be presented by rounding off to two decimal digits, except for the following situations (this applies to individual data and descriptive statistics):

$K_{el}$  and  $R_{sq}$  adjusted data: rounded off to four decimal digits.

PK parameter related to time such as  $T_{max}$ , must be reported with the same precision as the actual sampling time: rounded off to 3 decimal digits.

Concentration versus time data, as well as  $C_{max}$ : reported as they appear in corresponding dataset.

---

**12. Handling of Missing Data**

For safety,

- If an AE is recorded with an onset date corresponding to a dosing day, but the time is missing, then the AE will be assigned to the treatment phase planned treatment with a dosing planned that day.
- If an AE is recorded with an onset date that does not correspond to a dosing day, but the time is missing, then the AE will be assigned to the treatment phase planned treatment that covers the AE onset day.
- If an AE is recorded with an onset date where day and time are both missing, then the AE allocation to a treatment phase planned treatment will be done on a case by case basis considering available information (e.g. AE onset date, AE end date, AE comments, subject disposition).

For PK, only observed data will be used in the data analysis except for concentration values BLQ as described in Section 10.1. No attempt will be made to extrapolate or interpolate estimates for missing data.

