### 3.7 Subject Withdrawal and Replacement

Subjects will be advised that they are free to withdraw from the study at any time. Over the course of the study, the Sponsor and the Investigator or a designee may withdraw any subject from the study for one of the reasons described below; subject withdrawal will be done in accordance with the clinical site's SOP:

- safety reason;
- non-compliance with protocol requirements;
- significant protocol deviation;
- positive cotinine, alcohol, drug, or pregnancy test;
- vomiting within 3 hours (study Part 1) and 7 hours (study Part 2) after dosing.

Subjects excluded from dosing in one period as per criteria listed above, may be invited to participate in subsequent periods of the study if deemed appropriate by the Investigator and appropriate from a statistical standpoint (i.e. would permit adequate statistical comparison). However, subjects with positive cotinine, alcohol, or drug test will be definitively withdrawn from the study. Hematology results will be reviewed by the Investigator or designee prior to dosing in study Part 2 (Period 4). Subjects will be withdrawn from the study if it is deemed that

---

the subject's safety may be at risk on the basis of these test results. Subjects who withdraw or are withdrawn from study Part 1 after dosing, for reasons other than safety and tolerability, may be replaced after consultation between the Safety Committee members in order to assure initiating study Part 2 with 16 subjects. Such replacement resulting in dosing more subjects than planned in this protocol would be documented in a protocol amendment.

Subjects who withdraw or are withdrawn will be asked to remain at the clinic until the Investigator or a designee agrees that the subject is fine and can be discharged. As soon as subject withdrawal is confirmed, blood sampling will be stopped. A PK blood draw may be collected at the time of withdrawal if deemed required by the Investigator. Study exit procedures will be performed at the time of withdrawal from the study or as soon as possible thereafter.

---

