### 6.1 Safety Population

The safety population is defined as all subjects who received at least one dose of the study medication.

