### 9.2 Adverse Events

AEs will be recorded and evaluated for their seriousness, severity, and relationship to the study medication. AEs will be collected and documented during the course of the study and until 4 days following the last study drug administration, if reported. AEs will be followed-up until complete resolution, or until the Investigator judges it to be safe to discontinue follow-up. The relationship to the study medication will be classified according to the clinical site SOPs.

Treatment-emergent AEs and non-TEAEs (those occurring prior to administration of study medication or that first occurred prior to study drug administration and did not worsen in frequency or severity) will be listed. TEAEs will be defined as AEs that occur on or after the date and time of study drug administration, or those that first occur pre-dose but worsen by increase in occurrence or severity after study drug administration. AEs will also be documented if reported.

The incidence of TEAEs will be summarized using the safety population. The MedDRA® dictionary Version 23.1 will be used to classify all AEs reported during the study by SOC and PT.

Incidence of subjects who experienced TEAEs will be presented by treatment and overall, SOC, PT, by Investigator-assessed relationship and also by severity. Each subject may only contribute once to each of the incidence rates, for a TEAE following a given treatment, regardless of the number of occurrences; the highest severity or highest relationship will be presented, as appropriate. In each table, SOC will be presented in descending order of overall incidence rate in terms of frequency of subjects and then in frequency of events (alphabetical order will be used in case of equal rates). For each SOC, PT will be presented the same way.

Incidence of TEAEs (number of events) will also be presented by period(dose) and overall, by SOC, and PT, by Investigator-assessed relationship and severity.

Frequency of subjects experiencing Serious Treatment Emergent Adverse Events and Suspected Unexpected Serious Adverse Drug Reactions; and the number of events would be also summarized per treatment and overall. Also, these events and Serious Adverse Events (SAEs) will be listed per subject.

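### SAP 12 allocates adverse events without an onset time by planned rather than received treatment, so an event could be tabulated under a dose the subject missed

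*SAP*

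**What the plan says.** SAP 12 has three rules for adverse events with incomplete onset information.

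- Onset date on a dosing day, clock time missing: "but the time is missing, then the AE will be assigned to the treatment phase planned treatment with a dosing planned that day".
- Onset date on any other day, clock time missing: "then the AE will be assigned to the treatment phase planned treatment that covers the AE onset day".
- Day and time both missing: "then the AE allocation to a treatment phase planned treatment will be done on a case by case basis considering available information". Subject disposition is among the examples of information to consider, and only this rule mentions it.

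Planned and received treatment can differ. SAP 3.7, matching Protocol 9.11, states: "Subjects excluded from dosing in one period as per criteria listed above, may be invited to participate in subsequent periods of the study". This is subject to the Investigator's agreement and to statistical suitability. The listed criteria include a safety reason, non-compliance and a significant deviation.

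On the reporting side, SAP 9.2 says "TEAEs will be defined as AEs that occur on or after the date and time of study drug administration". It adds: "Incidence of subjects who experienced TEAEs will be presented by treatment and overall, SOC, PT, by Investigator-assessed relationship and also by severity". It counts each subject at most once per treatment, for an event after that treatment. Event counts are also shown by period (dose).

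SAP 5 refers to tabulation by treatment phase, but the term is not defined anywhere in the SAP.

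**The concern.** The first two rules in SAP 12 ask what was planned for the onset day. They do not ask whether the subject took it. The two questions have the same answer for every subject dosed in every period, but the plan itself provides for subjects who are not.

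For such a subject, an untimed event could enter the column of a dose never taken and be missing from the column of the dose last received. The by-dose tables are where a reader compares tolerability across 200, 500 and 1000 mg fasted and the fed dose. With about 24 subjects per column, one misplaced subject is visible.

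**Working it through.** The plan gives no figure to reproduce. The check is a reading of the rules on one constructed record, followed by a simple proportion.

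**Record.** A subject receives Treatment A (200 mg) in Period 1, is not dosed in Period 2 and is dosed again in Period 3. An adverse event has a known onset date but no clock time. The date is the scheduled Period 2 dosing day, or a later day before the Period 3 dose.

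**Is it treatment-emergent?** Yes. It starts after the first dose, so it meets the SAP 9.2 definition and must go into some treatment column.

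**Which column?** The answer depends on two undefined terms.

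| Meaning of dosing day | Meaning of treatment phase | Column |
|---|---|---|
| Scheduled day of the period | Scheduled period | B (500 mg, not received) |
| Subject's own dosing day, so the second rule applies | Scheduled period | B (500 mg, not received) |
| Subject's own dosing day, so the second rule applies | From one actual dose to the next | A (200 mg, received) |

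The event stays with the dose received only on the last reading, and that reading needs a definition the SAP does not contain. The word *planned* in the rules points to the first two.

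**Where can it arise?**

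- A missed Period 1 does not matter: before any dose the event is not treatment-emergent.
- A subject who misses Period 3 has not completed Part 1 and cannot enter Part 2.
- A missed Period 2 with return in Period 3 is therefore the clearest path.
- A subject withdrawn just before a planned dose can raise the same question without returning.

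**Size.** Inputs: 24 subjects in Part 1 (SAP 3.5). Assumption: one subject misses Period 2 and has one such event.

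- Subjects who received Treatment B: 24 − 1 = 23.
- Added to Treatment B incidence: 1/23 = 4.3 percentage points if the column is divided by subjects dosed, or 1/24 = 4.2 points if divided by 24.
- Removed from Treatment A incidence: 1/24 = 4.2 points, if the subject has no other event counted in that row under A.
- Two such subjects: 2/22 = 9.1 points on Treatment B.
- If allocation follows the last dose actually received: 0 events misplaced.

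The documents give no rate of missed periods or of missing onset times, so no expected number of misplaced events can be calculated.

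**The case against.** The best defence is that the wording is garbled rather than wrong. Treatment phase and planned treatment stand side by side like two alternative terms left in by mistake. If a phase was meant to run between actual doses, nothing is misplaced. SAP 9.2 also leans that way, because a subject never given 500 mg has no event after 500 mg. Actual doses and times are listed by subject under SAP 8.6, so a misplaced event could be found. This stands as a reason to call misallocation the natural literal reading and not a certainty. It does not remove the need for the definition.

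A reader might infer several stronger points that the documents do not support.

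- *SAP 9.2 and SAP 12 send the same event to different columns depending only on whether a time was recorded.* SAP 9.2 settles whether an event is treatment-emergent. Neither section gives a column rule for a timed event in an undosed period. That it would go to the last dose received is an inference from the counting rule.
- *Subjects who miss a period are the likeliest to have such an event.* Nothing shows this. An event that causes the missed dose would normally start before the scheduled day and so belong to the preceding dose on any reading.
- *Fed-dose rates will be understated by a third, because 16 subjects would be divided by 24.* "The incidence of TEAEs will be summarized using the safety population" names the analysis set and does not fix each column's denominator. The table shells are in a separate document, and an analyst would ordinarily use the number dosed.
- *Dose escalation is affected.* Protocol 7.5 bases escalation on review of the whole safety and tolerability data by the Safety Committee and the DSMB, not on these tables.

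**Conclusion.** The point holds as a defect of wording: read literally, SAP 12 could place an untimed event under a dose the subject did not receive. It needs both a missed dosing after the first dose and a missing onset time, and its frequency cannot be derived.

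If it happens, the effect is about 4 percentage points per misplaced subject in a by-dose column, assuming 24 subjects in Part 1 with one not dosed in that period. Overall counts stay the same. No safety inference is planned, and both study objectives are pharmacokinetic, so no formal conclusion is at risk. This is a free improvement.

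**What to change.** In SAP 12, replace planned treatment with treatment actually received:

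- Time missing, and the subject was dosed on the onset date: allocate to that dose.
- Time missing, and the subject was not dosed on the onset date: allocate to the most recent dose actually received. If there was none, class the event as not treatment-emergent.
- Day and time both missing: keep the case-by-case review, but choose only among doses the subject received.

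Define a treatment phase as running from one actual dose to the next, and apply the same definition to timed events so that both kinds follow one rule. As an optional clarification, SAP 9.2 could state that each treatment column's denominator is the number of subjects dosed with that treatment.

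The cost is a few sentences and one programming condition that uses the dosing records already listed under SAP 8.6. No new data are needed. For subjects dosed as planned, the allocation should not change, provided phases were meant to start at dosing.
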